The development and evaluation of the eNeighbor is grounded in a well-established conceptual model that has been used to successfully evaluate the efficacy of interventions for ADRD family caregivers.⁴⁹⁻⁵¹ The Stress Process Model (SPM) has been used extensively to study the manifestation of negative outcomes in dementia caregiving.⁵²⁻⁵⁵ The SPM is based on the mechanism of "proliferation," where the emotional stress of care provision to a person with dementia (primary stress) spreads to other life domains which are then posited to negatively influence global caregiving outcomes such as caregiver mental health or the person with ADRD's institutionalization. Psychosocial resources or formal service use may help stem stress proliferation and protect ADRD caregivers from negative outcomes.⁵³

The conceptual framework for the proposed project integrates constructs from the SPM. **Context of care** variables are conceptualized as key covariates; context of care considers key sociodemographic and background characteristics that may influence outcomes for persons with ADRD or their family caregivers. Similarly, **resource** variables such as perceptions of socioemotional support and community-based service use are considered as covariates in the eNeighbor conceptual model that could potentially alleviate negative outcomes. A final set of covariates considered in our conceptual model include **primary objective stressors**, or indices of dementia severity that may require greater day-to-day care provision on the part of family members. The proposed conceptual model positions eNeighbor as a key resource; the remote sensor technology of eNeighbor for dementia caregivers is hypothesized to independently and directly: **improve caregiver self-efficacy and competence, reduce caregiver distress** (subjective stress and depressive symptoms), **delay or reduce negative health transitions for the person with ADRD** (falls, wandering), and **delay or reduce the person with ADRD's service utilization** (residential care placement, hospitalization). The SPM is aligned with conceptualizations of

intervention effectiveness in the health information technology literature, suggesting that utilizing the SPM is appropriate when evaluating the efficacy of eNeighbor.⁵⁶

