The PI or research coordinators will call caregivers in the control group 48 hours following assignment to the usual care control group to address any questions they may have and to thank them for being part of the study and volunteering their time if no response from the participant in the usual care group is received following randomization). Group allocation (either attention control or treatment condition) will be based solely on their a priori randomization assignment number. The PI or research coordinators will then inform the ADRD caregiver of her/his group assignment within 2 days of baseline survey completion.

Following ADRD caregivers' enrollment into the proposed project and within 2 weeks of randomization to the eNeighbor treatment condition, the Director of Nursing and Technology (DNT) will schedule a visit at the home of the person with ADRD and the enrolled family caregiver. The DNT will oversee all system maintenance (battery changes, troubleshoot in instances where there is a loss of system contact), establish arrangements for other care services that are needed for the person with ADRD in instances of eNeighbor alerts or other health-related transitions, and develop and monitor a care plan with the family caregiver to ensure that it is effectively followed.

An initial Needs Assessment takes place to determine the best use and deployment of the eNeighbor remote sensor technology in the person with ADRD's home. The assessment begins with an identification of risk factors that suggest the need for remote health monitoring (e.g., the person with ADRD lives alone and has little supervision; the caregiver needs support; the person with ADRD has a history of falls or the caregiver has concerns with falls) as well as the use of other monitoring systems such as Safe Return™ or a similar device. The DNT will then discuss the results of the needs assessment with the ADRD caregiver and review how the remote monitoring system works, that the eNeighbor does not include cameras or microphones, is secure, and is private, and that the system learns the normal activities of the person with ADRD and alerts both the family caregiver and the DNT if something appears unusual (e.g., absence of expected ADL behaviors). Following this operational overview, the DNT will summarize the secure and password-protected MyHealthsense website, which is used by the family caregiver or other

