The Needs Assessment form and utilization data collected by the DNT based on the Healthsense/eNeighbor remote health sensor system will be securely transferred to [name] and RC via a secure University of Minnesota Box file transfer procedure. Any hard copy Needs Assessment forms or similar utilization data will be maintained in a locked file cabinet at The Lutheran Home Association. As one of the analyses proposed will focus on the individualization/customization of the eNeighbor system for each family as well as variable utilization data based on the alerts issued by the remote monitoring system and follow-up contacts by the DNT, these utilization data will be collected throughout the 18-month evaluation period for each caregiver and person with ADRD.

5.3 Follow-Up:

Follow-up will continue until Month 55, resulting in a 53-month data collection period. Eligible ADRD caregivers will be interviewed/surveyed at baseline and every 6 months thereafter for up to 18 months. Six-month follow-up interviews/surveys will be completed by the PI or research coordinators for all participants in the treatment and control conditions. The selected measures have strong psychometric properties, sensitivity to change, and clinical relevance in the evaluation of remote health monitoring technology as established in the stress process and

PROTOCOL TITLE: A Proactive Health Monitoring Intervention for Dementia Caregivers: The eNeighbor

related conceptual models. Caregivers will complete the proposed measures at each time point (context of care items will be collected at baseline only). Baseline and follow-up interviews will take place at a location and in a format that is convenient to ADRD caregivers (at the University of Minnesota Delaware Clinical Research Unit, the ADRD caregivers' home or through online, telephone or mail formats if desired). Each follow-up interview is expected to take approximately 45 minutes to complete. Information from the follow-up surveys will also be utilized to complete the E-Neighbor Disposition Form at each follow-up interval. As the information on the Disposition form is available from the follow-up surveys, the PI or RCs can extract and complete the Disposition form following the completion each 6-, 12-, and 18-month survey.

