9.0 Study Population

9.1 Inclusion Criteria:

The following inclusion criteria will be applied for 200 persons with ADRD: 1) English speaking; 2) physician diagnosis of ADRD (Alzheimer's disease, Lewy Body disease, fronto-temporal dementia, or stroke/vascular dementia; mild cognitive impairment only); 3) not currently receiving care or case management services; and 4) 55 years of age and over. Caregivers of persons with ADRD must: 1) speak English; 2) be 21 years of age and over; 3) self-identify as someone who provides help to the person with ADRD because of their cognitive impairments; 4) self-identify as the person most responsible for providing hands-on care to the person with ADRD; 5) plan to remain in the area for at least 18 months in order to reduce possible loss to follow-up; and 6) indicate a willingness to use eNeighbor.

9.2 Exclusion Criteria: Anyone who does not fit the inclusion criteria will be excluded.

9.3 Screening: If caregivers agree to participate, the PI or research coordinators will initiate a brief screening procedure applying the inclusion criteria above.

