Our proposed analyses will provide in-depth tests of Hypotheses 1 and 2 and partially test Hypothesis 3 (i.e., rates of change in ADRD caregivers’ self-efficacy, competence, subjective stress, depressive symptoms, and frequency of negative health transitions and service use). In one set of outcome evaluations, the baseline value will be included as a covariate, and time will be “centered” at 6-months post-baseline. This scales the intercept effect to be a main effect of eNeighbor group assignment and allows the eNeighbor treatment and the attention control groups to have different 6-, 12-, and 18-month change trajectories, or an expanded eNeighbor treatment*time interaction effect. After establishing that the individual growth parameter estimates have significant variance around the mean trajectories of change in key dependent variables, an eNeighbor treatment vs. attention care control group indicator will be added as the key independent variable to predict intercepts and rates of change in outcomes. Additional analyses will determine if covariates (e.g., stress process model covariates including context of care indicators, primary objective stressors, and resources) significantly vary across the eNeighbor treatment and attention control groups at baseline and over time via growth curve modeling procedures. If statistically significant variations between the eNeighbor treatment and

PROTOCOL TITLE: A Proactive Health Monitoring Intervention for Dementia Caregivers: The eNeighbor

control groups are found, initial status and rate of change parameters for these covariates will be included in all tests to provide additional statistical control.

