Cox proportional hazard survival analyses will determine whether participation in the eNeighbor treatment group results in significantly less time to nursing home admission (e.g., admission into a 24-hour nursing home facility for at least 90 days), overnight hospitalization, emergency room use, and negative health transitions (falls, wandering) when compared to persons with ADRD in the attention control group (Specific Aim 1/Hypothesis 3). The Cox proportional hazards model is defined as the product of an unknown function of time and the exponent of a linear combination of risk variables. eNeighbor treatment vs. attention control group membership will be the independent variable of interest in the test of Hypothesis 3; time to nursing home admission, overnight hospitalization, emergency room use, and occurrence of a fall or a wandering event will serve as the dependent variables. Date of randomization will serve as baseline. Additional variables will serve as covariates, including time-invariant and time-varying measurements of stress process covariates. Likelihood ratio tests and partial odds ratios will be examined in order to determine the degree to which these variables explain the observed effects of eNeighbor on time to dependent variable occurrence.

Variations in eNeighbor Use and Setting

Empirical treatment fidelity data and context of care measures that assess heterogeneity in the use of eNeighbor within the treatment condition (e.g., frequency and duration of sensor alerts and myHealthsense website use; diverse home characteristics) will be included as a series of additional Specific Aim 1 analyses. These analyses will explore the effects of variations in eNeighbor use on the outcomes hypothesized above for persons with ADRD and their family caregivers.

Specific Aim 1/Hypothesis 4

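### Tests of Hypotheses 1–3 may be adjusted for post-randomisation change in covariates such as service use, so the reported coefficient may not be the randomised effect

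*Combined protocol and SAP*

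**What the plan says.** **Growth models (section 17.3, Hypotheses 1, 2 and part of 3).** The arm indicator is entered first. Further analyses then ask whether the stress-process covariates (resources, primary objective stressors and context of care) "significantly vary across the eNeighbor treatment and attention control groups at baseline and over time via growth curve modeling procedures". Where a significant difference appears, "initial status and rate of change parameters for these covariates will be included in all tests to provide additional statistical control".

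**Cox models (section 17.3, rest of Hypothesis 3).** "Additional variables will serve as covariates, including time-invariant and time-varying measurements of stress process covariates". No significance condition is attached.

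**Which covariates.** Section 2.3 says that resource "variables such as perceptions of socioemotional support and community-based service use are considered as covariates in the eNeighbor conceptual model". It treats dementia-severity indices as the primary objective stressors.

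**When they are measured.** Section 5.3 has the measures repeated at every wave and restricts only the context-of-care items to baseline.

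**What the plan does not say.** Nowhere is a model with arm alone, or with arm and baseline covariates only, named as the primary test of Hypotheses 1–3. The models containing covariate change are not labelled as mediation or sensitivity analyses.

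**The concern.** A baseline covariate cannot be affected by treatment, so adjusting for context of care or for initial status is harmless here. A covariate's rate of change, or its value at 6 or 12 months, can be affected. If treatment moves it, and it influences the outcome or shares a cause with it, conditioning on it changes what the arm coefficient means.

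The protocol describes both links for community service use:

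- **Treatment to covariate.** In the eNeighbor arm the Director of Nursing and Technology will "establish arrangements for other care services that are needed for the person with ADRD in instances of eNeighbor alerts" (section 5.2). Entrants must be "not currently receiving care or case management services" (section 9.1), so later use of those services arises after randomisation.
- **Covariate to outcome.** "Psychosocial resources or formal service use may help stem stress proliferation and protect ADRD caregivers from negative outcomes" (section 2.3).

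No comparable treatment pathway is described for dementia severity or socioemotional support.

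The trigger makes matters worse. A difference between arms over time is what a treatment effect on the covariate produces, so the rule fires most often when adjustment does most damage. It reaches the primary outcomes in section 3.1, caregiver self-efficacy and competence. The cost-effectiveness analysis under Hypothesis 4 is not affected.

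**Working it through.** **Inputs from section 17.2.** Effect 0.50 SD, alpha 0.05 (two-sided assumed), power 0.80, 200 caregivers, 20% attrition. Completers: 200 × 0.80 = 160, or 80 per arm.

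**The plan's own figure.** n per arm = 2(1.960 + 0.842)² / 0.50² = 62.8, so 63 per arm and 126 in total. With attrition, 126 / 0.80 = 157.5, so 158. The stated 200 is not reproduced, but it is larger and therefore sufficient. Power at 80 per arm is Φ(0.50/√(2/80) − 1.960) = Φ(1.20) = 0.885. This mismatch does not bear on the point.

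**Assumed, because the documents give no values.** Treatment shifts the covariate by δ = 0 to 0.5 SD. The covariate–outcome coefficient b, or the residual correlation r, is 0.3 to 0.5. One covariate is modelled at a time.

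**What adjustment does.**

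- *Mediated effect:* M = δT + u and Y = (0.50 − bδ)T + bM + e. The total effect is 0.50, but with M in the model the arm coefficient is 0.50 − bδ. For δ = b = 0.3 this is 0.41; for δ = b = 0.5 it is 0.25.
- *No effect on the outcome, shared cause:* M = δT + u and Y = ru + e. The true effect is 0, but with M in the model the arm coefficient is −rδ. For δ = r = 0.5 this is −0.25 SD.

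**How often the rule fires.** Approximately Φ(δ/√(2/80) − 1.975). For δ = 0.3 this is Φ(−0.08) = 0.47; for δ = 0.5 it is Φ(1.19) = 0.88.

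**Simulation of the written rule** (80 per arm, 8,000 trials per setting; M is added only if it differs by arm at p < .05). Without the rule, power is 88% and type I error 5%. In each range the first value is for coefficient 0.3 and the second for 0.5. Estimate and power come from the mediated model, type I error from the shared-cause model.

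| Shift δ (SD) | Rule fires | Mean estimate (true 0.50) | Power | Type I error |
|---|---|---|---|---|
| 0 | 5% | 0.50 | 89% | 4–5% |
| 0.2 | 24% | 0.47–0.45 | 85–84% | about 5–6% |
| 0.3 | 47% | 0.44–0.40 | 80–75% | 7–12% |
| 0.5 | 88% | 0.36–0.27 | 62–45% | 15–38% |

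**Direction.** At δ = 0.5 and r = +0.5, almost all the false rejections go against eNeighbor. At r = −0.3 to −0.5, 14–38% of null trials reject in its favour.

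**Four-wave version** (covariate intercept and slope added when the slopes differ by arm; slope reliability 0.6 and 0.9). It is somewhat milder. At shifts 0.2, 0.3 and 0.5 the estimates are 0.48–0.46, 0.46–0.41 and 0.40–0.29; power is 86–84%, 82–76% and 69–48%; type I error is 5–6%, 6–10% and 10–31%.

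**Cox version** (100 per arm, 18 months, assumed hazard ratio 0.60, about 94 events, time-varying covariate always in the model). Without the covariate the hazard ratio is 0.61–0.62 and power 62–67%. With it they are 0.63–0.64 and 59–58% at shift 0.2, and 0.65–0.69 and 50–43% at shift 0.5. Type I error is at most about 8%. With 700 trials per setting, these powers carry a simulation standard error of about 2 points: √(0.6 × 0.4 / 700) = 0.019.

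**The case against.** **The randomised comparison is already in the plan.** Section 17.3 enters the arm indicator before the covariate step, and adjustment is conditional. This is true, and an unadjusted estimate would probably exist. But once the trigger is met the rule covers every test, and nothing says which estimate decides the hypothesis.

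**The Cox paragraph is explanatory.** It speaks of how far the covariates account for eNeighbor's observed effects, which implies an earlier model without them. This stands in part, and the Cox results are the mildest. Still, the sentence adding the covariates is unconditional, and no arm-only or baseline-only Cox model is named as the test.

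**The pathway is documented for one covariate and partly inferred.** The service-use instrument is not described, and repeat measurement is read from a general statement. This stands, and it limits what can be said about likelihood. It does not change what the rule permits.

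**The large figures need large shifts.** A 0.5 SD shift equals the whole effect the trial is sized to detect. At 0.1 SD power is about 88% and type I error 4–5%. This stands: material harm begins at about 0.3 SD.

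**The type I error figures use a shared cause that the documents do not describe.** The documented link is mediation. If services rise and protect, adjustment shrinks the estimate, which is conservative for a claim of benefit. This stands. Loss of a real effect is the better supported risk, and false rejections are a further possibility.

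**The simulations are not the plan's exact model.** Neither growth simulation includes the intercept effect centred at 6 months. This also stands, and the figures are illustrations. The algebra above applies to any arm coefficient conditioned on a covariate that treatment has moved.

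**Conclusion.** The concern holds. As written, section 17.3 allows the tests of Hypotheses 1–3, including those on the primary outcomes, to condition on covariate change that treatment may have caused, and it protects no randomised comparison as primary. The size cannot be taken from the documents. Under the stated assumptions it runs from no harm when treatment leaves the covariate alone, through a small loss at a 0.2 SD shift, to a mean estimate of 0.36–0.27 SD in place of 0.50 and power of 62–45% at a 0.5 SD shift. Direction depends on the signs of the two links, so the rule could hide a real effect or, with a shared cause, produce a spurious one. The rate-of-change rule in the growth models is the stronger part of the point and the Cox covariates the weaker. This should be fixed before analysis.

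**What to change.** In section 17.3:

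1. Delete the significance-triggered covariate rule. Its baseline part is not a source of this bias, but a list fixed in advance replaces it without any data-driven choice.
2. Name as primary for the growth analyses: arm, time, arm-by-time, the baseline value of the outcome, and a short prespecified list of baseline covariates.
3. Name as primary for the Cox analyses: arm and a baseline list of the same kind.
4. Remove rate-of-change and time-varying covariates from these tests. Report models that contain them separately, labelled as mediation or exploratory analyses.

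Simply naming the existing arm-only model as primary would meet most of the concern, but it would conflict with a rule that still applies to all tests, so the rule should go too.

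The cost is wording in 17.3 only: no new data and no new participants. The covariate-change analyses are kept under a label that matches what they estimate.

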PROTOCOL TITLE: A Proactive Health Monitoring Intervention for Dementia Caregivers: The eNeighbor

trusted family members and friends to coordinate and share information regarding appointments or the well-being of the person with ADRD. The remote monitoring system will then be installed in the person with ADRD's home and the expected performance thresholds and daily routines will be programmed. The DNT will monitor sensor performance throughout the duration of the project, and if these sensors are damaged or become inoperable, she will replace these sensors as needed free of charge.

A particularly important aspect of eNeighbor is its configuration in homes with varying broadband internet service. If broadband services are available at the person with ADRD's home, connection of the sensors involves the simple addition of a wireless router which connects with the existing broadband modem in the person with ADRD's home (and is included in the remote sensor package that will be supported by the proposed project). If broadband is not available, the current project will support connectivity for the person with ADRD's home via purchase of this service as a "bundle" through an existing telephone or cable TV plan. In the instance the family caregiver does not wish to utilize broadband service options for the purposes of eNeighbor, the proposed project will support a low data rate cellular service plan that supports only eNeighbor functions. The quality of data collection is identical across cellular or broadband modalities. The DNT will then share paper versions of the alert system reports generated by the MyHealthsense website.

To address environmental diversity, the DNT will collect information on the approximate square footage of the house; number of bedrooms and bathrooms; distances between primary bathroom (e.g., the one used to shower/bathe in), living room area (e.g., where television or the majority of similar leisure activity takes place), and entryway; and number of levels in the home.

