We will take several steps to address attrition bias. If a person with ADRD has moved into a residential long-term care facility or has died, caregiver follow-up interviews will include queries determining when these events occurred. Regular follow-up will continue in order to collect as much information on outcome variables that are appropriate (i.e., intention to treat principle). Per the consent form, participants will have the opportunity to provide a Social Security Number for the care recipient to study staff (over the phone) during/at the end of the study. Participants may also choose to opt out of this. At the conclusion of the project, Thank You cards will be mailed to all participants to ensure rapport.

Treatment fidelity. Monthly system reviews will take place through system reports generated by the Director of Nursing and Technology. The MyHealthsense portal can also track how often the ADRD caregiver or others utilize the care coordination resources of MyHealthsense. The PI or research coordinator will also determine the degree to which participants apply the eNeighbor monitoring tool to their everyday care situations. An online or mail survey of close-ended, Likert-scale items to determine eNeighbor's acceptability by ADRD caregivers as well as multiple open-ended questions will be administered to all ADRD caregivers in the eNeighbor treatment condition at the 6-, 12-, and 18-month interview intervals. The open-ended responses will provide qualitative data as to the reasons why family caregivers felt the health monitoring technology of eNeighbor was or was not easy to utilize (e.g., "Why or how was the health monitoring technology easy or difficult to use?" The identification of these barriers or facilitators will be considered when examining ADRD caregivers' perceptions of eNeighbor's design, delivery, and ease of use.

Final Study Visit/Survey.

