The final study visit will operate similar to the other follow-up interviews/surveys. Following completion of the final 18-month assessment, participants in the treatment group will be informed of the conclusion of the study and the need to remove the health monitoring sensors. However, available eNeighbor sensor packages purchased for this demonstration project will also be offered to the control group on a first-come, first-serve basis at the conclusion of the randomized control trial evaluation phase as stated in the consent form. If the eNeighbor system is found to have an overall negative effect (specifically, the eNeighbor system results in greater emotional stress or depressive symptoms on the part of the caregiver) then the eNeighbor system will not be offered on a first-come, first-serve basis for those in the control group. The latter is now included to provide additional clarification in the consent form. For those not selected but who desire the health monitoring technology, the project team will work with HealthSense to determine if discounts are available and applicable.

Post-evaluation semi-structured interviews. Thirty semi-structured interviews with ADRD caregivers in the e-Neighbor treatment condition will take place. These interviews will take place a month after completion of the final 18-month follow-up interview for selected participants. The PI and [name] (the Co-I) will identify 15 ADRD caregivers who indicated positive acceptance on the embedded qualitative and quantitative 6-, 12-, and 18-month system reviews and 15 ADRD caregivers who reported low acceptance on the embedded qualitative and quantitative 6-, 12-, and 18-month system reviews.

A stratified purposive sampling approach will also be applied; the PI and [name] will purposively identify ADRD caregivers of varying kin relationship (spouse vs. adult child), dementia severity (middle versus late stage dementia symptomatology), caregiver gender, and racial or ethnic background to participate in the post-RCT semi-structured interviews.

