The cost-effectiveness of the remote monitoring technology intervention will be assessed by comparing costs of implementation and healthcare utilization between persons with ADRD in the treatment condition and those in the attention control. The analysis will be conducted from the perspective of the payer (i.e., the public). Costs in the numerator of the incremental cost-effectiveness ratio (ICER) will be determined by identifying the differences in Medicare and Medicaid expenditures for persons with ADRD across the eNeighbor treatment and attention control groups using aggregated (“rolled up”) Medicare and Medicaid claims matched to the individual participant by Social Security number for the 18 months of participation. Because the differences in costs derive from a randomized trial, an evaluation of the difference in mean costs can determine significance. In addition, the direct costs of the intervention will be included as the cost of the remote sensor hardware, staff time (i.e., the Director of Nursing and Technology, who will track her hourly effort related to monitoring eNeighbor activities and assisting ADRD caregivers over a 1.5-year period), and installation costs over the 18-month study period.

The differences in effectiveness included in the denominator of the ICER will be measured using 5 ADRD caregiver and person with ADRD outcome measures: a) the standard cut-point of

“moderate or higher” burden on the Zarit Burden Interview;⁷⁷ b) the standard cut-point of “major depression” on the Center for Epidemiological Studies Depression scale;⁷⁸ c) fall (occurred or not); d) wandering event (occurred or not); e) nursing home admission (placed or not); f) hospitalization (overnight use or not); and g) emergency room use (used or not). Significant differences in cost will be investigated. Sensitivity analysis will be performed where parameter uncertainty exists. Where possible, evaluation of these ICERs will be based on comparisons in prior literature to determine the overall costs and effectiveness of eNeighbor.

Analysis: Specific Aim 2

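### Hypothesis 4 tests mean costs as a randomised comparison, but claims can be linked only through an optional Social Security number given almost always after allocation is known; its cost list also does not name project-paid connectivity

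*Combined protocol and SAP*

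**What the plan says.** The Hypothesis 4 part of section 17.3 builds the numerator of the incremental cost-effectiveness ratio (ICER) from two parts.

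- **Healthcare cost.** This is the difference in Medicare and Medicaid expenditure, from claims matched to each participant by SSN over the 18 months. The comparison is justified in one sentence: "Because the differences in costs derive from a randomized trial, an evaluation of the difference in mean costs can determine significance".
- **Intervention cost.** "the direct costs of the intervention will be included as the cost of the remote sensor hardware, staff time" of the Director of Nursing and Technology, and installation.

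The stated viewpoint is: "The analysis will be conducted from the perspective of the payer (i.e., the public").

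Three other places bear on this.

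- Section 5.3 (attrition bias paragraph) gives participants the "opportunity to provide a Social Security Number for the care recipient to study staff (over the phone) during/at the end of the study", and adds: "Participants may also choose to opt out of this".
- Section 5.2 has caregivers told their arm within 2-3 days of the baseline interview in one place, and within 2 days in another.
- Section 5.2 also covers internet access: "If broadband is not available, the current project will support connectivity for the person with ADRD's home via purchase of this service". Where the caregiver does not want broadband, "the proposed project will support a low data rate cellular service plan that supports only eNeighbor functions".

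**The concern.** Randomisation supports an unadjusted comparison of mean costs among everyone randomised. Here the costs are observed only for people who can be linked, and whether they can be linked depends on a choice made, almost always, after the caregiver knows the arm. If that choice relates to cost differently in the two arms, the linked means can differ when there is no effect. If it relates to cost in the same way in both arms, the test is sound under no effect, but a true saving can look smaller or larger than it is.

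The protocol gives some reason to think that willingness or opportunity could differ. Section 5.3 has monthly calls to treated dyads, while controls are called around survey times. Deaths and moves into residential care, which the same section anticipates, may relate both to cost and to whether anyone is available to give a number late in the study.

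The connectivity point is separate. A cellular plan that serves only eNeighbor is a cost of delivering eNeighbor, and if it is not counted the intervention looks cheaper than it was.

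At stake is the ICER numerator. Section 1.0 states Hypothesis 4 as a hypothesis, but section 3.0 lists no cost outcome as primary or secondary.

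**Working it through.** The plan gives no cost, linkage or connectivity figure, so there is no number of its own to reproduce. The check is a comparison of passages, followed by illustrations from assumed inputs.

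**Passages side by side**

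1. Costs need an SSN (17.3). The SSN is optional and is requested during or at the end of the study (5.3). The arm is known within 2-3 days of baseline (5.2). A request in those few days is not strictly ruled out, but almost all collection must fall after allocation is known.
2. The safeguard in 17.3 is sensitivity analysis for parameter uncertainty. The intention-to-treat remark in 5.3 concerns follow-up interviews. The text available does not say how unlinked people are handled.
3. The cost list in 17.3 has three items. The router is part of the sensor package (5.2). The recurring broadband or cellular charge is not plainly hardware, staff time or installation. The public-payer viewpoint is not given as a reason to omit it, and the list does count sensor hardware, which 5.3 describes as "available eNeighbor sensor packages purchased for this demonstration project".

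**Notation for the illustrations**

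- p: share of people who are high-cost
- c: their cost relative to the others
- d and o: linkage rates of high-cost people and of others
- True mean: T = (1-p) + pc
- Linked mean: M = [(1-p)o + pdc] / [(1-p)o + pd]

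Assumed: p = 0.10 or 0.20, c = 2 or 4, and 80 of 100 people linked per arm. The 80% borrows the 20% attrition in section 17.2 as a stand-in. SSN refusal is a different process, so true linkage could be lower or higher.

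**A. No true effect, overall linkage 80% in both arms**

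- Linked high-cost share: q = pd/0.8
- Bias = p × gap × (c-1)/0.8, where gap is the difference in d between arms
- SE = (c-1) × √{[q₁(1-q₁) + q₀(1-q₀)]/80}

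Example: p = 0.20, c = 4, d = 0.70 against 0.50. Then q = 0.175 and 0.125, bias = 0.05 × 3 = 0.15, and T = 1.6, so the bias is 9.4% of T. SE = 3 × √{(0.1444 + 0.1094)/80} = 0.169, so the bias is 0.89 SE.

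With d between 0.40 and 0.90:

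| Gap in d | Spurious difference, % of T | In SE |
|---|---|---|
| 0 | 0 | 0 |
| 10 points | 1.1-4.7 | 0.26-0.50 |
| 20 points | 2.3-9.4 | 0.53-0.96 |
| 30 points | 3.4-14.1 | 0.82-1.39 |

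The sign reverses if the other arm links better. The SE multiples are upper limits, because cost variation within the two groups is ignored.

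**B. True effect, same d and o in both arms**

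The high-cost share falls from 20% to 15% or 10%, or from 10% to 8% or 5%. o is set so that the control arm links at 80%.

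Example: 20% to 10%, c = 4, d = 0.40. Then o = (0.80 - 0.08)/0.80 = 0.90. The linked means are 1.300 and 1.141, a difference of 0.159 against a true 0.30, which is 53%.

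| d | Share of true saving shown by linked data |
|---|---|
| 40% | 51-55% |
| 60% | 76-79% |
| 80% | 100% |
| 90% | 110-112% |

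Equal linkage rates in the two arms therefore do not rule out distortion.

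**Cross-check of A with a different model.** Cost and willingness to give the SSN are taken as jointly normal with correlation ρ, with 100 per arm, no true difference and a nominal 5% test. The mean cost among those linked is ρφ(k)/u, where u is uptake and k = Φ⁻¹(1-u).

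- Uptake 70% in both arms, same ρ: no bias, type I error 5.0%.
- Uptake 80% against 50%: bias 0.13 SD and error 11.9% at ρ = 0.3; 0.22 SD and 26.8% at ρ = 0.5.
- Uptake 70% in both arms, ρ = 0.3 in one arm and 0 in the other: 0.15 SD and 14.5%.

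**C. Connectivity.** At an assumed $20-60 a month, 18 months cost 18 × $20 = $360 to 18 × $60 = $1,080 per supported home. If 10-40% of homes need it, that is $36-432 per treated dyad.

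**The case against.** **On linkage.** The randomisation sentence can be read as the usual reason for comparing arms without confounder adjustment; it does not claim complete linkage. The sensitivity analysis in 17.3 could be stretched to cover incomplete linkage, though it does not say so. Section 5.3 introduces the SSN request by reference to the consent form, whose pages are not available here, so its wording cannot be judged. Every magnitude above is assumed. The largest null bias, 1.39 SE, would not reach significance by itself, although it would raise the false-positive rate. All of this stands as a limit on what can be claimed. None of it restores the randomised comparison among those linked.

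**On connectivity.** Section 17.3 opens by referring to implementation costs in general, which might be meant to include the service charge, and the public-payer viewpoint might be a reason to omit it. It also applies only to homes without broadband or whose caregiver declines it. So the item is unnamed rather than excluded, and it is probably small.

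**Stronger readings that the documents do not support**

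- A reader might infer that the cost comparison is biased, or biased in eNeighbor's favour. Nothing shows who gave an SSN, so neither existence nor direction can be stated.
- A reader might infer that claims exist only for people who give the number. Claims exist regardless; only linkage depends on it.
- A reader might infer that the plan deliberately leaves connectivity out. The text is unclear and shows no such decision.

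**Conclusion.** The point holds as a limited one. Following section 17.3 as written would compare a subset formed almost entirely after allocation as if it were the randomised groups, with no stated handling of the rest. Whether this biases the result, by how much and in which direction, is unknown. The illustrations show only that moderate differential linkage could produce spurious differences of a few to about 14% of mean cost, and that equal linkage rates are not enough reassurance. They rest on the assumed high-cost share, cost ratio and linkage rates.

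If the cost list is followed literally, intervention cost is understated, probably by a small amount. If implementation costs were meant to include connectivity, only the wording needs repair.

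Only Hypothesis 4 is affected. Hypotheses 1-3 do not use claims or intervention costs and are untouched.

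**What to change.** In the Hypothesis 4 part of section 17.3:

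1. Add the broadband and cellular amounts that the project pays to the intervention cost in the ICER numerator, from project payment records.
2. Qualify the randomisation sentence so that it refers to all those randomised, and report the number linked in each arm.
3. Compare linked with unlinked dyads within each arm on baseline data and on caregiver-reported hospital, emergency room and nursing home use. The surveys offered to withdrawn caregivers under section 13.2 may extend these data.
4. Add a sensitivity analysis that weights linked dyads by the inverse of their estimated probability of linkage, using those data. State that it corrects only for selection explained by what was observed.

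Asking for the still-optional SSN before randomisation would be cleaner for new dyads. It would need a consent and script amendment, and it is probably moot, since section 8.0 ends the project on 3/30/2019.

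Cost: one cost line, a short analysis paragraph and a little more analysis work, with no new data collection. The ICER may look slightly less favourable.
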